5.4.5.3 Management of cytokine release syndrome in monotherapy and combination therapy arms

CRS clinically manifests when large numbers of lymphocytes (B lymphocyte cells, T cells, and/or NK cells) and/or myeloid cells (macrophages, dendritic cells, and monocytes) become activated and release inflammatory cytokines. CRS has classically been associated with therapeutic mAb infusions, most notably anti-CD3 (OKT3), anti-CD52 (alemtuzumab), anti-CD20 (rituximab), and the CD28 super-agonist, TGN1412. In these settings, symptom onset typically occurs within minutes to hours after the infusion begins. CRS has also been reported following administration of bi-specific antibodies for leukemia, infusion of haploidentical mononuclear cells to patients with refractory leukemia, and adoptive immunotherapies for cancer, most notably T cells engineered to express chimeric antigen receptors.³⁸

It is important to distinguish CRS from infection, tumor lysis syndrome, primary phagocyte lymphohistiocytosis/macrophage activation syndrome, hypersensitivity/allergic reaction(s), or other inflammatory disorders. Additional tests such as autoimmune serology may be used to determine a possible immunogenic etiology.

The study will be conducted in sites experienced in immune-oncology clinical studies including the management of CRS. Patients will be monitored for signs and symptoms of CRS for all cycles of treatment with ANV419. Following study drug(s) infusion during dose escalation (the Combination Dose Finding part), all patients will undergo a 23-hour observation period. Clinical monitoring will be conducted per individual sites institutional standards within the framework of observation required for this Protocol, including monitoring of vital signs every 2 hours for the first 8 hours, and 20 hours post end of infusion in Cycles 1 and 2 (only). After Cycle 2, the observation period will lessen to 90 minutes post end of infusion, provided no additional safety concerns have been identified. Safety observation measures may be added or removed, at the discretion of the SRC, upon review of all safety data for the study. Patients may require observation beyond 23 hours if ≥Grade 3 AE and/or requires medical intervention and prolonged medical observation. In both arms of the Monotherapy Dose Expansion part (Arms A1 and A2) and Combination Dose Expansion part (Arms B and C), all patients will be monitored for 90 minutes or longer post end of infusion from Cycle 1, depending on whether additional safety concerns have been identified in Part 2. Patients will be monitored per individual site institutional standard during administration of ANV419 in combination with pembrolizumab or ipilimumab. It is optionally recommended (not mandatory) that patients stay in close proximity to the site and are accompanied by a caregiver when possible, for whom accommodations will be provided. Based on emerging data, the SRC may still decide that it is in the best interest of the patients to increase monitoring or observation durations, or mandate hospitalization.

Grading of CRS should follow the criteria specified in Table 17.

Table 17: Management of CRS per NCI CTCAE Version 5.0

Grade	Treatment
Grauc	- Vigilant supportive care.
	- Additional diagnostic testing should be performed to rule out differential diagnoses. If an
	infection cannot be ruled out with certainty, start of an empiric antibiotic therapy should
	be considered.
Grade 1:	- Treat fever and neutropenia if present, monitor fluid balance, administer anti-pyretics
Fever with or	and analgesics as needed.
without	- All patients with early signs of CRS should be regularly evaluated for signs of further
constitutional	deterioration.
symptoms	- No actions or hold ANV419 treatment until symptoms subside.
	- Vigilant supportive care.
	- Hold study drug(s). Restart once CRS resolves to Grade ≤1.
	- For subsequent infusions, increase infusion duration and consider premedication with
	antihistamines such as Benadry1® and an H ₂ blocker.
	Hypoxia:
	- Supplemental oxygen.
	- Tocilizumab or siltuximab ± corticosteroids and supportive care, as recommended for the
	management of hypotension.
	Hypotension:
	- IV fluid bolus of 500 to 1000 mL of normal saline.
	- Can give a second IV fluid bolus if SBP remains <90 mmHg.
	- Tocilizumab 8 mg/kg IV or siltuximab 11 mg/kg IV for the treatment of hypotension that
	is refractory to fluid boluses; tocilizumab can be repeated after 6 hours if needed.
	If hypotension persists after 2 fluid boluses and anti-IL-6 therapy:
	- Start vasopressors, consider hospitalization, obtain echocardiogram, and initiate other
	methods of hemodynamic monitoring.
Grade 2:	- In patients at high-risk or if hypotension persists after 1 to 2 doses of antiIL6 therapy,
-Hypotension	dexamethasone can be used at 10 mg IV every 6 hours.
responding to	- Manage fever and constitutional symptoms as in Grade 1.
fluids	Organ toxicity:
-Hypoxia	- Symptomatic management of organ toxicities, as per standard guidelines.
responding to	- Consider tocilizumab or siltuximab ± corticosteroids and supportive care, as indicated
$<40\% O_2$	for hypotension.
	- Vigilant supportive care.
	- Permanently discontinue study drugs(s) treatment.
	- Patient should be hospitalized for a minimum of a 24-hour observation period.
	Hypoxia:
	- Supplemental oxygen including high-flow oxygen delivery and non-invasive positive
	pressure ventilation.
	- Tocilizumab or siltuximab ± corticosteroids and supportive care, as described above.
	Hypotension:
	- IV fluid boluses as needed, as recommended for the treatment of Grade 2 CRS.
	- Tocilizumab and siltuximab as recommended for Grade 2 CRS, if not administered
Grade 3:	previously.
-Hypotension	- Vasopressors as needed.
managed with	- Consider transfer to ICU, obtain echocardiogram, and perform hemodynamic monitoring
1 pressor	as in the management of Grade 2 CRS.
-Hypoxia	- Dexamethasone 10 mg IV every 6 hours; if refractory, increase to 20 mg IV every
requiring	6 hours.
≥40% O ₂	- Manage fever and constitutional symptoms as indicated for Grade 1 CRS.

Table 17: Management of CRS per NCI CTCAE Version 5.0 (Continued)

Grade	Treatment
Grade 3	
(Continued):	
-Hypotension	
managed with	
1 pressor	
-Hypoxia	Organ toxicity:
requiring	- Symptomatic management of organ toxicities, as per standard guidelines.
≥40% O ₂	- Tocilizumab or siltuximab ± corticosteroids and supportive care, as described above.
	- Vigilant supportive care.
	- Permanently discontinue study drug(s) treatment.
	- Patient should be hospitalized for a minimum of a 24-hour observation period.
	Hypoxia:
	- Mechanical ventilation.
	- Tocilizumab or siltuximab ± corticosteroids and supportive care, as described above.
	Hypotension:
	- IV fluids, anti-IL-6 therapy, vasopressors, and hemodynamic monitoring as defined for the management of Grade 3 CRS.
	N. 4. 1. 1. 1. 2. /1. 737
	 Methylprednisolone 1 to 2 g/day IV. Manage fever and constitutional symptoms as indicated for Grade 1 CRS.
	- Manage level and constitutional symptoms as indicated for Grade 1 CKs.
	Organ toxicity:
Grade 4:	- Symptomatic management of organ toxicities, as per standard guidelines.
-Life-threatening	- Tocilizumab or siltuximab \pm corticosteroids and supportive care, as described above.
consequences	- In cases where neither tocilizumab, siltuximab, nor glucocorticoids are effective, other
-Urgent	immunosuppressants such as the T cell-depleting antibody therapies, including
intervention	alemtuzumab and ATG, IL1R-based inhibitors (anakinra) or cyclophosphamide might be
indicated	of benefit.

 $ATG = \text{antithymocyte globulin}; \ CRS = \text{cytokine release syndrome}; \ H_2 = \text{histamine}; \ ICU = \text{intensive care unit}; \ IL = \text{interleukin}; \ IV = \text{intravenous(ly)}; \ NCI \ CTCAE = \text{National Cancer Institute Common Terminology Criteria for Adverse Events}; \ O_2 = \text{oxygen}; \ SBP = \text{systolic blood pressure}; \ T \ \text{cell} = \text{thymus lymphocyte cell}.$

Source: U.S. Department of Health and Human Services. National Institutes of Health. National Cancer Institute. Common Terminology Criteria for Adverse Events (CTCAE). Version 5.0. 27 November 2017

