5.4.5 Dose Modification Guidelines

AEs (both serious and non-serious) potentially related to ANV419, pembrolizumab, or ipilimumab may represent an immunologic etiology. These AEs may occur shortly after the first dose or several months after the last dose.

If a patient experiences TEAEs that may be related to ANV419 alone or in combination with pembrolizumab or ipilimumab, ANV419 doses might be reduced if applicable, interrupted, or permanently discontinued and all changes must be reported in the Case Report Form (CRF). All ≥Grade 3 AEs considered possibly, probably, or definitely related to study drug(s) must be

discussed with the Investigator and Sponsor. During Cycle 1, dose interruption should be avoided if a patient has not experienced a ≥Grade 2 TEAE related to study drug. In subsequent cycles, dose interruptions and/or discontinuation are permissible following discussion between the Investigator and the Sponsor or designee.

5.4.5.1 Dose Modification and Management Guidelines for adverse events related to ANV419 in Monotherapy Arms

General principles

Common adverse events that have been reported with ANV419 include, but are not limited to pyrexia, liver enzyme elevations, lymphopenia, nausea/vomiting, and low-grade CRS. Appropriate supportive care or pre-medication is recommended to manage ANV419 related side effects, and to maintain ANV419 dose-intensity.

For patients enrolled in Arm A1 (), dose reduction is not permitted but modification of infusion rate and/or dose delay is allowed in the event of ANV419 related toxicities. For patients enrolled in Arm A2 (), dose reduction to is permitted in addition to modification of infusion rate and/or dose delay. Dose re-escalation of ANV419 to the randomized dose can be considered for AEs that are self-limiting and under close monitoring. If re-escalation is not tolerated, then ANV419 should be reinstated at reduced dose.

Treatment may be delayed for up to ______ to allow for resolution of ANV419 related toxicities and for up to ______ for non-ANV419 related/unexpected toxicities (i.e., hip fracture). If treatment cannot be resumed within this time frame, the patient will be permanently discontinued from study.

The section below provides specific guidelines for the management of related ANV419 toxicities. The recommendations are not intended to serve as rigid guidelines or to replace clinical judgement.

Pyrexia

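### Table 17 puts a vasopressor step in the Grade 2 CRS cell, under hold-and-restart and optional admission, although its own grade column makes hypotension on one pressor Grade 3

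*Protocol*

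**What the plan says.** Protocol 5.4.5.3 covers CRS in the monotherapy and combination arms. It makes the table the grading standard: "Grading of CRS should follow the criteria specified in Table 17".

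- **Grade 2 row.** The label is hypotension that responds to fluids, or hypoxia that responds to less than 40% oxygen. The study-drug action is "Hold study drug(s). Restart once CRS resolves to Grade ≤1". The treatment steps run from a fluid bolus to a second bolus, then to tocilizumab or siltuximab when boluses fail. After that comes "If hypotension persists after 2 fluid boluses and anti-IL-6 therapy", and the instruction there is "Start vasopressors, consider hospitalization, obtain echocardiogram, and initiate other" forms of hemodynamic monitoring.
- **Grade 3 row.** The label is hypotension managed with one pressor, or hypoxia needing at least 40% oxygen. The actions are "Permanently discontinue study drugs(s) treatment" and "Patient should be hospitalized for a minimum of a 24-hour observation period". The row refers back to Grade 2 for anti-IL-6 treatment ("Tocilizumab and siltuximab as recommended for Grade 2 CRS, if not administered" earlier) and for hemodynamic monitoring.

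Other rules use the line between Grades 2 and 3:

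- Protocol 7.1.4 makes Grade 3 and Grade 4 CRS, but not Grade 2, an AESI with a form due within 24 hours.
- Protocol 5.4.5 says that all "≥Grade 3 AEs considered possibly, probably, or definitely related to study drug(s) must be" discussed with the Investigator and Sponsor.
- SAP 3.8.1.1 tabulates AESIs, and TEAEs by maximum severity.

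**The concern.** For one clinical situation, CRS hypotension on a single vasopressor, the table prints two sets of instructions. The Grade 2 cell makes admission optional and allows study drug to resume. The Grade 3 row requires admission and ends study treatment.

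A site working down the Grade 2 cell reaches the pressor step without being told that the patient has left Grade 2. It could treat admission as discretionary and later rechallenge a patient for whom the protocol's own definition requires permanent discontinuation. If the event also stayed recorded as Grade 2, it would be missing from the AESI tables and understated in the maximum-severity tables. The AESI form and the Sponsor discussion for related Grade 3 or higher events would not be triggered on grade.

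**Working it through.** The plan states no figure on this point, so the main check is a side-by-side reading of Table 17.

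| For a patient started on one pressor | Grade 2 cell | Grade 3 row |
|---|---|---|
| Study drug | Hold, restart at Grade 1 or lower | Stop permanently |
| Hospital | Consider | At least 24 hours |
| AESI (7.1.4) | No | Yes, form within 24 hours |
| Pointer to the other row | None forward to Grade 3 | Back to Grade 2 |

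**Is the row placement an extraction artefact?** No. The treatment block for each grade opens with the same supportive-care line, which separates the blocks. The Grade 3 row also asks for hemodynamic monitoring as under Grade 2, and that monitoring appears only at the pressor step. The step therefore belongs to the Grade 2 cell.

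**Does the cell match its own label?** Not beyond the first steps. The label is hypotension that responds to fluids, yet the cell goes on to treat hypotension that does not, and then adds a pressor.

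**Can the two rows be reconciled?** On grading, yes: the grade column controls, so one pressor means Grade 3. On the instructions, no. If starting the pressor moves the patient to Grade 3, admission is already required, and the Grade 2 instruction to consider it can never apply.

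**How often might this arise?** The only data are from study ANV419-001 (Protocol 1.3.4, Table 1; Appendix F, Table 25), with N = 34. Intervals are exact Clopper-Pearson 95% limits. The last column multiplies each rate and limit by 30, the Part 1 maximum. It assumes full enrollment and the same rates (the Part 1 doses are redacted).

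| Drug-related event | ANV419-001 | 95% CI | × 30 |
|---|---|---|---|
| Grade 3 or higher CRS | 1/34 = 2.9% | 0.07% to 15.3% | 0.9 (0.02 to 4.6) |
| Hypotension, any grade | 4/34 = 11.8% | 3.3% to 27.5% | 3.5 (1.0 to 8.2) |

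Table 1 lists no Grade 3 or higher drug-related hypotension. Neither row of figures measures the affected group, which is CRS with pressor-treated hypotension recorded or handled as Grade 2. The first counts events already graded 3 or higher. The second is not tied to CRS or to pressors, and it is not a strict ceiling, because hypotension may be recorded under the CRS term. Pressor use is not reported, so the affected number cannot be computed.

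**The case against.** The strongest reply is that the protocol already settles the matter. A patient on a pressor no longer meets the Grade 2 label, the grade column governs, and the Grade 2 steps read as an escalation ladder. The Grade 3 row's references back to Grade 2 treatment support that reading. Severity is in any case graded by NCI CTCAE version 5.0 (7.1.3), the source named for Table 17. This stands as far as the correct grade goes.

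Several further points also stand and limit the consequences:

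- When the pressor is started, both rows withhold study drug. They diverge only at rechallenge.
- Many such events would be SAEs, reportable within 24 hours (7.2, 7.3), the same clock as the AESI form.
- Under 5.4.5, dose interruptions after Cycle 1 follow discussion with the Sponsor, whatever the grade.
- Sites are experienced in CRS, and the Safety Review Committee can mandate hospitalization.
- Section 5.4.5.1, which sends monotherapy CRS to Table 17, says its guidance is not rigid and does not replace clinical judgement. Section 5.4.5.3, which contains the table, does not repeat this.

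None of this makes optional admission or restart the right instruction for a patient on a pressor.

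A reader might infer more: that the grade of such an event is undetermined, or that Part 1 events were misgraded and AESIs missed. The documents support neither. The grade is determined, and nothing shows that any site recorded a wrong one. Nor can an effect on dose-limiting toxicities be claimed, because those criteria are redacted.

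**Conclusion.** The point holds as a conflict of instructions within Table 17, not as a gap in the grading rule. At the pressor step the Grade 2 cell gives a weaker hospital instruction and a rechallenge rule that contradicts the Grade 3 row, and it does not direct the reader there.

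The size is small. Few if any patients are affected, and the ANV419-001 rates do not bound the number. ORR, the go/no-go rules and the SAP's count of Grade 2 or higher CRS do not change. Only AESI and maximum-severity summaries could change, and only if a pressor-treated event had been left at Grade 2. SAP section 1 records the decision of 27 February 2024 to stop after Part 1, so little prospective effect remains in this study. What remains is a data check and the wording if the table is reused. It should be corrected because it concerns patient safety and the correction is cheap.

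**What to change.** **Table 17.** Reword the pressor step in the Grade 2 cell along these lines: if a vasopressor is needed, the event is at least Grade 3; start vasopressors and follow the Grade 3 (or Grade 4) row, including permanent discontinuation, hospitalization for at least 24 hours and AESI reporting. The words *at least* matter because a patient on a pressor may meet Grade 4. Keep the echocardiogram and hemodynamic-monitoring instructions, but move them to the Grade 3 row. That row now refers back to Grade 2 for them, so simply deleting the step would leave the reference empty.

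**Part 1 data.** Compare CRS events recorded as Grade 2 with vasopressor entries in the concomitant-medication data. Query mismatches with the investigator before database lock, or report them in the Clinical Study Report if the database is already locked. SAP 3.3.7 already lists concomitant medications by patient, and SAP 3.8.1.1 already lists AE grade. The CRS-treatment summary names only corticosteroids and tocilizumab individually, so it should not be relied on to show pressors.

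**Cost.** A short edit to one table and one cross-check of data already collected, with no new visits, procedures, tables or listings. The downside is that Grade 3 CRS and AESI counts may rise slightly, and where the table is reused a few patients would not be rechallenged.

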5.4.5.4 Management of adverse events in combination arms

AEs associated with pembrolizumab or ipilimumab exposure may represent an immunologic etiology. These irAEs may occur shortly after the first dose or several months after the last dose of pembrolizumab/ipilimumab treatment and may affect more than 1 body system simultaneously. Therefore, early recognition and initiation of treatment is critical to reduce complications. Based on existing clinical study data, most irAEs were reversible and could be managed with interruptions of pembrolizumab or ipilimumab, administration of corticosteroids, and/or other supportive care. For suspected irAEs, ensure adequate evaluation to confirm etiology or exclude other causes. Additional procedures or tests such as bronchoscopy, endoscopy, or skin biopsy may be included as part of the evaluation. Based on the severity of irAEs, withhold or permanently discontinue pembrolizumab/ipilimumab, and administer corticosteroids. Consultation with disease-specific specialists should be considered. Dose modification and toxicity management guidelines for irAEs associated with pembrolizumab and ipilimumab are provided in Table 18 and Table 19, respectively.

Attribution of toxicity and holding study drugs

When study drugs are administered in combination, attribution of an AE to a single component is likely to be difficult. Therefore, while the Investigator may attribute a toxicity event to the combination, to ANV419 alone, to pembrolizumab alone, or to ipilimumab alone, for AEs listed in Table 18 and Table 19, both interventions must be held according to the criteria in Table 18 and Table 19.

For AEs that occur with the combination of ANV419 and pembrolizumab or ANV419 and ipilimumab that clearly can be attributed to ANV419, please refer to Section 5.4.5 for management guidelines and recommended dose modifications to be taken for ANV419.

For combination arms of this study, both drugs should be held until the attribution of an irAEs can be fully analyzed and has resolved to baseline or ≤Grade 1. In general, ≥Grade 3 TEAEs in the combination treatment arms will result in discontinuation of both ANV419 and pembrolizumab or ANV419 and ipilimumab, but, in rare instances, continuing either ANV419, pembrolizumab, or ipilimumab may be allowed where clinical benefit can be documented after resolution of toxicity to baseline or ≤Grade 1. In the event that a toxicity results in holding ANV419, pembrolizumab, ipilimumab, or the combination of ANV419 and pembrolizumab or the combination of ANV419 and ipilimumab for >42 days, the drugs should be permanently discontinued for that patient.

Table 18. Dose Modification for ANV419 in Combination With Pembrolizumab

Table 10. Dose		UI AITTI	ii Combination	vitn Pembrolizu	mab
	Grade			Corticosteroid	
	(NCI CTCAE	Action with	Action with	and/or Other	Monitoring and
irAEs	Version 5.0)	ANV419	Pembrolizumab	Therapies	Follow-Up
Pneumonitis	Grade 2 Recurrent Grade 2, Grade 3 or 4	Withhold. Upon resolution to ≤Grade 1, may resume study treatment. Withhold study treatment. Upon resolution to ≤Grade 1, may resume study treatment 1 dose level	Withhold. Upon resolution to ≤Grade 1, may resume study treatment. Permanently discontinue.	Administer corticosteroids (initial dose of 1 to 2 mg/kg prednisone or equivalent) followed by taper. Add prophylactic antibiotics for opportunistic infections.	Monitor participants for continuing signs and symptoms of pneumonitis. Evaluate participants with radiographic imaging
Diarrhea/colitis	Grade 2 or 3 Recurrent Grade 3 or Grade 4	Withhold. Upon resolution to ≤Grade 1, may resume study treatment. Permanently discontinue.	Withhold. Upon resolution to ≤Grade 1, may resume study treatment. Permanently discontinue.	Administer corticosteroids (initial dose of 1 to 2 mg/kg prednisone or equivalent) followed by taper.	imaging. Monitor participants for continuing signs and symptoms of enterocolitis (ie, diarrhea, abdominal pain, blood or mucus in stool with or without fever) and of bowel perforation (ie, peritoneal signs and ileus). Participants with ≥Grade 2 diarrhea suspected colitis should consider GI consultation and performing endoscopy to rule out colitis. Participants with diarrhea/colitis should be advised to drink liberal quantities of clear fluids. If sufficient oral fluid intake is not feasible, fluid and electrolytes should be substituted via IV infusion.

Table 18. Dose Modification for ANV419 in Combination With Pembrolizumab (Continued)

	G 1		I		
	Grade (NCI CTCAE	Action with	Action with	Corticosteroid and/or Other	Monitoring and
irAEs	Version 5.0)	ANV419	Pembrolizumab	Therapies	Follow-Up
AST or ALT elevation or increased bilirubin	Grade 2 ⁰	Withhold. Upon resolution to ≤Grade 1, may resume study treatment.	Withhold. Upon resolution to ≤Grade 1, may resume study treatment.	Administer corticosteroids (initial dose of 0.5 to 1 mg/kg prednisone or equivalent) followed by taper.	Monitor with liver function tests (consider weekly or more frequently until
	Grade 3 ⁰ or 4 ⁰	Permanently discontinue.	Permanently discontinue.	Administer corticosteroids (initial dose of 1 to 2 mg/kg prednisone or equivalent) followed by taper.	liver enzyme value returned to baseline or is stable).
T1DM or hyperglycemia	New onset T1DM or Grade 3 or 4 hyperglycemia associated with evidence of β-cell failure	Withhold. Upon resolution to ≤Grade 1, may resume study treatment.	Withhold. ⁰	Initiate insulin replacement therapy for participants with T1DM. Administer antihyperglycemic in participants with hyperglycemia.	Monitor participants for hyperglycemia or other signs and symptoms of diabetes.
Hypophysitis	Grade 2 Grade 3 or 4	Withhold. Upon resolution to ≤Grade 1, may resume study treatment. Withhold or permanently discontinue.	Withhold. Upon resolution to ≤Grade 1, may resume study treatment. Withhold or permanently discontinue. ⁰	Administer corticosteroids and initiate hormonal replacements as clinically indicated.	Monitor for signs and symptoms of hypophysitis (including hypopituitarism and adrenal insufficiency).
Hyperthyroidism	Grade 2 Grade 3 or 4	Withhold or permanently discontinue. ⁰	Continue. Withhold or permanently discontinue.	Treat with nonselective beta-blockers (eg, propranolol) or thionamides as appropriate.	Monitor for signs and symptoms of thyroid disorders.
Hypothyroidism	Grade 2, 3 or 4	Continue.	Continue.	Initiate thyroid replacement hormones (eg, levothyroxine or liothyronine) per Standard of Care.	Monitor for signs and symptoms of thyroid disorders.

Table 18. Dose Modification for ANV419 in Combination With Pembrolizumab (Continued)

	Grade			Corticosteroid	
	(NCI CTCAE	Action with	Action with	and/or Other	Monitoring and
irAEs	Version 5.0)	ANV419	Pembrolizumab	Therapies	Follow-Up
Nephritis: grading according to increased creatinine or acute kidney injury	Grade 2 Grade 3 or 4	Withhold. Upon resolution to ≤Grade 1, may resume study treatment. Permanently discontinue.	Withhold. Upon resolution to ≤Grade 1, may resume study treatment. Permanently discontinue.	Administer corticosteroids (prednisone 1 to 2 mg/kg or equivalent) followed by taper.	Monitor changes of renal function.
Neurological toxicities	Grade 2 Grade 3 or 4	Withhold. Upon resolution to ≤Grade 1, may resume study treatment. Permanently discontinue.	Withhold. Upon resolution to ≤Grade 1, may resume study treatment. Permanently discontinue.	Based on severity of AE, administer corticosteroids.	Ensure adequate evaluation to confirm etiology and/or exclude other causes.
Myocarditis	Grade 2, 3 or 4	Permanently discontinue.	Permanently discontinue.	Based on severity of AE, administer corticosteroids.	Ensure adequate evaluation to confirm etiology and/or exclude other causes.
Exfoliative dermatologic conditions	Suspected SJS, TEN, or DRESS Confirmed SJS, TEN, or DRESS	Withhold. Permanently discontinue.	Withhold. Permanently discontinue.	Based on severity of AE, administer corticosteroids.	Ensure adequate evaluation to confirm etiology or exclude other causes.
All other irAEs	Persistent Grade 2	Withhold. Upon	Withhold. Upon resolution to	Based on severity of AE, administer	Ensure adequate evaluation to

Anaveon AG Clinical Study Protocol ANV419-101

		resolution to ≤Grade 1, may resume study treatment.	≤Grade 1, may resume study treatment.	corticosteroids.	confirm etiology or exclude other causes.
	Grade 3	Withhold or discontinue based on the event. ⁰	Withhold or discontinue based on the event. ⁰		
	Recurrent Grade 3 or Grade 4	Permanently discontinue.	Permanently discontinue.		

Table 18. Dose Modification for ANV419 in Combination With Pembrolizumab (Continued)

Note: Non-irAEs will be managed as appropriate, following clinical practice recommendations.

AST/ALT = >3 to $5 \times \text{ULN}$ if baseline is normal; >3 to $5 \times \text{baseline}$, if baseline is abnormal; bilirubin: >1.5 to $3 \times \text{ULN}$ if baseline is normal; >1.5 to $3 \times \text{baseline}$ if baseline is abnormal.

AST/ALT: >5 to $20 \times$ ULN if baseline is normal; >5 to $20 \times$ baseline, if baseline is abnormal; bilirubin: >3 to $10 \times$ ULN if baseline is normal; >3 to $10 \times$ baseline if baseline is abnormal.

AST/ALT: $>20 \times$ ULN if baseline is normal; $>20 \times$ baseline, if baseline is abnormal; bilirubin: $>10 \times$ ULN if baseline is normal; $>10 \times$ baseline if baseline is abnormal.

The decision to withhold or permanently discontinue pembrolizumab is at the discretion of the Investigator or treating physician. If control is achieved or resolution to \leq Grade 2, pembrolizumab may be resumed.

Events that require discontinuation include, but are not limited to, encephalitis and other clinically important irAEs (eg, vasculitis and sclerosing cholangitis).

AE = adverse event; ALT = alanine aminotransferase; AST = aspartate aminotransferase; DRESS = drug reaction with eosinophilia and systemic symptoms; GI = gastrointestinal; irAE = immune-related adverse event; IV = intravenous(ly); NCI CTCAE = National Cancer Institute Common Terminology Criteria for Adverse Events; SJS = Stevens-Johnson syndrome; T1DM = type 1 diabetes mellitus; TEN = toxic epidermal necrolysis; ULN = upper limit of normal.

Source: Keytruda®. Package Insert. Merck Sharp & Dohme Corp; 2014

Table 19. Dose Modification for ANV419 in Combination With Ipilimumab

	C 1			C 4: 4 :1	
	Grade			Corticosteroid	
	(NCI CTCAE	Action with	Action with	and/or Other	Monitoring and
irAEs	Version 5.0)	ANV419	Ipilimumab	Therapies	Follow-Up
Pneumonitis	Grade 2 Recurrent Grade 2, Grade 3 or 4	Withhold. Upon resolution to ≤Grade 1, may resume study treatment. Withhold study treatment. Upon resolution to ≤Grade 1, may resume study treatment 1 dose level lower.	Withhold. Upon resolution to ≤Grade 1, may resume study treatment. Permanently discontinue.	Administer corticosteroids (initial dose of 1 to 2 mg/kg prednisone or equivalent) followed by taper. Add prophylactic antibiotics for opportunistic infections.	Monitor participants for continuing signs and symptoms of pneumonitis. Evaluate participants with radiographic imaging.

Table 19. Dose Modification for ANV419 in Combination With Ipilimumab (Continued)

Table 19. Dose	Modification 10	or AN V 419 in	Combination V	Vith Ipilimumab	(Continuea)
irAEs Diarrhea/colitis	Grade (NCI CTCAE Version 5.0) Grade 2 Recurrent Grade 3 or Grade 4	Action with ANV419 Withhold. Upon resolution to ≤Grade 1, may resume study treatment.	Action with Ipilimumab Withhold. Upon resolution to ≤Grade 1, may resume study treatment.	Corticosteroid and/or Other Therapies Administer corticosteroids (initial dose of 1 to 2 mg/kg prednisone or equivalent) followed by taper.	Monitoring and Follow-Up Monitor participants for continuing signs and symptoms of enterocolitis (ie, diarrhea, abdominal pain, blood or mucus in stool with or without fever) and of bowel perforation (ie, peritoneal signs and ileus). Participants with ≥Grade 2 diarrhea suspected colitis should consider GI consultation and performing endoscopy to rule out colitis. Participants with diarrhea/colitis should be advised to drink liberal quantities of clear fluids. If sufficient oral fluid intake is not feasible, fluid and electrolytes should be substituted via IV infusion.
AST or ALT elevation or increased bilirubin	AST/ALT >3 to 5 × ULN or total bilirubin is more than 1.5 × and up to 3 × ULN AST/ALT >5 × ULN or total bilirubin is more than 3 × ULN	Withhold. Upon resolution to ≤Grade 1, may resume study treatment. Permanently discontinue.	Withhold. Upon resolution to ≤Grade 1, may resume study treatment. Permanently discontinue.	Administer corticosteroids (initial dose of 0.5 to 1 mg/kg prednisone or equivalent) followed by taper. Administer corticosteroids (initial dose of 1 to 2 mg/kg prednisone or equivalent) followed by taper.	Monitor with liver function tests (consider weekly or more frequently until liver enzyme value returned to baseline or is stable).

Table 19. Dose Modification for ANV419 in Combination With Ipilimumab (Continued)

Table 19. Dose	Modification id	or AN V 419 in	Combination v	Vith Ipilimumab	(Continued)
	Grade			Corticosteroid	
	(NCI CTCAE	Action with	Action with	and/or Other	Monitoring and
irAEs	Version 5.0)	ANV419	Ipilimumab	Therapies	Follow-Up
Endocrinopathies	Grade 2, 3, or 4	Withhold. Upon resolution to ≤Grade 1, may resume study treatment.	Withhold if not clinically stable.	Treatment with replacement or interventions as appropriate.	Monitor for signs and symptoms of endocrinopathies.
Hypophysitis ¹	Grade 2, 3, or 4	Withhold. Upon resolution to ≤Grade 1, may resume study treatment.	Withhold. Resume when acute symptoms have resolved.	Administer corticosteroids and initiate hormonal replacements as clinically indicated.	Monitor for signs and symptoms of hypophysitis (including hypopituitarism and adrenal insufficiency).
Nephritis: with renal dysfunction	Grade 2 or 3 increased blood creatinine Grade 3 or 4	Withhold. Upon resolution to ≤Grade 1, may resume study treatment. Permanently discontinue.	Withhold. Upon resolution to ≤Grade 1, may resume study treatment. Permanently discontinue.	Administer corticosteroids (prednisone 1 to 2 mg/kg or equivalent) followed by taper.	Monitor changes of renal function.
Neurological toxicities ²	Grade 2 Grade 3 or 4	Withhold. Upon resolution to ≤Grade 1, may resume study treatment. Permanently discontinue.	Withhold. Upon resolution to ≤Grade 1, may resume study treatment. Permanently discontinue.	Based on severity of AE, administer corticosteroids.	Ensure adequate evaluation to confirm etiology and/or exclude other causes.
Myocarditis	Grade 2 Grade 3 or 4	Withhold. Upon resolution to ≤Grade 1, may resume study treatment. Permanently discontinue.	Withhold. Upon resolution to ≤Grade 1, may resume study treatment. Permanently discontinue.	Based on severity of AE, administer corticosteroids.	Ensure adequate evaluation to confirm etiology and/or exclude other causes.
Exfoliative or bullous dermatologic conditions	Grade 2 Grade 3 or 4	Withhold until specialist assessment. Permanently discontinue.	Withhold until specialist assessment. Permanently discontinue.	Based on severity of AE, administer corticosteroids.	Ensure adequate evaluation to confirm etiology or exclude other causes.

Table 19. Dose Modification for ANV419 in Combination With Ipilimumab (Continued)

				, ich ipilinamas	(
irAEs	Grade (NCI CTCAE Version 5.0)	Action with ANV419	Action with Ipilimumab	Corticosteroid and/or Other Therapies	Monitoring and Follow-Up
Ophthalmologic	Grade 2, 3, or 4 that does not improve to Grade 1 within 2 weeks while receiving topical therapy or that requires treatment	Withhold or discontinue based on the event.	Permanently discontinue.	Based on recommendation by ophthalmologist.	Ensure evaluation by ophthalmologist and continue to follow up as clinical indicated.
All other irAEs	Persistent Grade 2 Grade 3 Recurrent Grade 3 or Grade 4	Withhold. Upon resolution to ≤Grade 1, may resume study treatment. Withhold or discontinue based on the event. Permanently discontinue.	Withhold. Upon resolution to ≤Grade 1, may resume study treatment. Withhold or discontinue based on the event. Permanently discontinue.	Based on severity of AE, administer corticosteroids.	Ensure adequate evaluation to confirm etiology or exclude other causes.

Note: Non-irAEs will be managed as appropriate, following clinical practice recommendations.

- 1. Signs of mass effect, including headache, photophobia, or visual field cuts.
- 2. Permanently discontinue ipilimumab if signs of encephalitis or respiratory insufficiency due to neurological toxicity regardless of grade.

AE = adverse event; ALT = alanine aminotransferase; AST = aspartate aminotransferase; GI = gastrointestinal; irAE = immune-related adverse event; IV = intravenous(ly); NCI CTCAE = National Cancer Institute Common Terminology Criteria for Adverse Events; ULN = upper limit of normal.

Source: Yervoy®. Package Insert. Bristol-Myers Squibb Company; 2011

